9.6 Procedural Pain

Not Applicable.

9.7 Safety Subgroup Analyses

Not Applicable.

9.8 Other Safety Analyses

The numbers and percentage of subjects with device deficiencies will be summarized by suspect device type.

A listing will be provided for device deficiencies for the Safety Population.

10.0 Other Analyses

Not applicable.

11.0 Interim Analyses

Not applicable.

12.0 Overall Type-I Error Control

Not applicable.

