## 11 Statistical Methods

### 11.1 General Statistical Considerations

A brief summary of the general statistical analysis methods is provided below; full details will be provided in a separate statistical analysis plan (SAP), which will be finalized prior to database lock.

Data will be summarized using descriptive statistics (number of observations [n], mean, standard deviation, median, minimum, and maximum for continuous variables; and n and percent for categorical variables).

Hypothesis testing will be performed at 0.025 significance level (1-sided). Conclusions related to study outcomes will be focused on the overall results of each outcome.

Two critical time points, baseline and end of study, will be referenced in most of statistical analyses for this study. Baseline is defined as the latest assessment prior to any study treatments for each subject. End of study is the last clinical visit an enrolled subject has in this study, V7 (after approximately 5 months of treatment). Subjects who discontinue prematurely will be asked to return for the last clinical visit for end-of-study data collection.

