2.4 Sample Size Determination

A sample size of 48 subjects will provide 90% power to detect if change from baseline to end of study visit in the FACE-Q™: Satisfaction with Facial Appearance Overall Scale Rasch-transformed score is different from zero, assuming a mean change of 12.0 and a standard deviation of 25.0.

This calculation is based on a one-sample, 1-sided t-test at 0.025 significance level. The assumptions of mean and standard deviation are based on FACE-Q™ results from the HARMONY Study GMA-CMB-14-001. Anticipating a potential 20% drop-out rate (for early withdrawals and/or subjects who failed to duly complete the FACE-Q™: Satisfaction with Facial Appearance Overall Scale assessment at end of study), 60 subjects will be enrolled.

PASS 2008 software was used to calculate the sample size.

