4.2 Subgroup

Subgroup analysis will be performed for the primary efficacy analysis by gender, as male and female subjects may have differing expectations/perceptions of aesthetic improvement; they will be examined separately.

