8.0 Efficacy Analyses

8.1 General Considerations

- All efficacy analyses will be conducted in the Evaluable Population.
- Day 1 is defined as the day on which the study treatment is first received.
- Baseline for efficacy is defined as the last non-missing assessment on or prior to Day 1.
- Study day is relative to Day 1.
- Change from baseline will be computed as post-baseline minus baseline.

- Categorical variables will be summarized descriptively using number of subjects with observed values or events (n) and the percentage of subjects with observed values or events.
- Continuous variables will be summarized descriptively using number of subjects with observed values (n), mean, standard deviation (SD), standard error of mean (SEM), median, minimum (min), and maximum (max).
- Unless otherwise specified, the estimated mean and median for a set of values will be printed out to 1 more significant digit than the original values; the SD and SEM will be printed out to 2 more significant digits than the original values; the min and max will report the same significant digits as the original values.
- Shapiro-Wilks test will be used to check the normality assumption. If the normality assumption is met, the statistical hypothesis test will be performed based on one-sample, one-sided t-test at 0.025 significance level. If the normality assumption is not met, Wilcoxon signed-rank test will be used instead and a 97.5% confidence interval (CI) for the median will be presented using the Hodges Lehmann method. Shapiro-Wilks and Wilcoxon signed-rank test will be performed by proc univariate procedure, and Hodges Lehmann CI of the median for paired samples will be performed based on a SAS macro by Han (2008) [\[1\]](#) as specified in SPP Section 3.3.
- All CIs will be 1-sided 97.5% CIs, and will be printed to 2 decimal places, unless stated otherwise. P-values output will be in the format: ‘0.xxxx’, where xxxx is the value rounded to 4 decimal places. Every p-value less than 0.0001 will be presented as <0.0001. If the p-value is returned as >0.9999, then present it as it is.
- Unless otherwise specified, the summaries will be provided by treatment group, gender, and overall.

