8.4.2 Secondary Efficacy Analyses

Change from baseline in the Rasch-transformed score of FACE-Q™ questionnaires (FACE-Q™: Aging Appraisal, FACE-Q™: Psychological Function, FACE-Q™: Social Function, FACE-Q™: Satisfaction with Skin) will be summarized descriptively by treatment group, gender, and overall and will be analyzed using a one sample t-test (or Wilcoxon signed-rank test if normality assumptions are not met) for the Evaluable Population. See SPP Appendix D, Appendix E, Appendix F, and Appendix G for the calculation of the overall Rasch-transformed score for each FACE-Q™ questionnaire.

The number and percentage of subjects who provide responses to each FACE-Q™ questionnaire will also be summarized descriptively by treatment group, gender, and overall, for the Evaluable Population, based on the following categories for each questionnaire:

- FACE-Q™ Aging Appraisal
 - 1. Definitely Agree
 - 2. Somewhat Agree
 - 3. Somewhat Disagree
 - 4. Definitely Disagree
- FACE-Q™ Psychological Function, FACE-Q™ Social Function
 - 1. Definitely Disagree
 - 2. Somewhat Disagree
 - 3. Somewhat Agree
 - 4. Definitely Agree
- FACE-Q™ Satisfaction with Skin
 - 1. Very Dissatisfied
 - 2. Somewhat Dissatisfied
 - 3. Somewhat Satisfied
 - 4. Very Satisfied

For the Self-Perception of Age (SPA) questionnaire, the number and percentage of subjects who look their current age will be summarized for baseline and the final study visit by treatment group, gender, and overall, for the Evaluable Population. The change from baseline in the number of years look younger and older to the final study visit will be summarized descriptively by treatment group, gender, and overall, for the Evaluable Population.

A shift table to summarize the changes into an improvement category from the baseline to the final study visit will be provided in frequency and percentage. No statistical testing for the shift table will be performed.

There are two assessment categories in GAIS at the final study visit: subject rating and investigator rating. Descriptive summaries will be provided in frequency and percentage of the scales at the final study visit, in the 5-point scale from -2 to +2 by treatment group, gender, and overall, for the Evaluable Population. The scales include:

- 2: Much Improved
- 1: Improved
- 0: No Change
- -1: Worse
- -2: Much Worse

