Descriptive summaries will be provided in frequency and percentage for nine questions of PAAQ at baseline and the final study visit by treatment group, gender, and overall, for the Evaluable Population, with five categories of answers for each question. Five categories of answer include:

- 0. Never
- 1. Rarely
- 2. Some of the Time
- 3. Most of the Time
- 4. All of the Time

The PAAQ will also be summarized in the transformed total score and three domains, using descriptive statistics by treatment group, gender, and overall and will be analyzed using a one-sample t-test (or Wilcoxon signed-rank test if normality assumption is not met) for the Evaluable Population.

The transformed scale score is calculated as $[(\text{actual raw score} - \text{lowest possible raw score}) / \text{possible raw score range}] * 100$. This formula can be simplified as $[(\text{actual raw score} - 0) / 4] * 100$.

The transformed total score is calculated as [(actual total raw score - lowest possible total raw score) / (possible total raw score range)] * 100. This formula can be simplified as [(actual total raw score - 0) / 36] *100.

Three domains include psychological domain, appearance domain, and coping domain. The psychological domain is defined as (sum of transformed scale score in PAAQ questions of 2, 4, 6, 7, and 8) / (number of questions). This formula can be simplified as (sum of transformed scale score in PAAQ questions of 2, 4, 6, 7 and 8) / 5.

Similar manner will be applied to the appearance domain and the coping domain, but with different number of PAAQ questions included for each domain. The appearance domain includes PAAQ questions of 1, 3 and 5. The coping domain contains only PAAQ question 9. See SPP Appendix H for the details of domain score calculation and missing data imputation.

Listings will be provided for FACE-Q™: Aging Appraisal, FACE-Q™: Psychological Function, FACE-Q™: Social Function, FACE-Q™: Satisfaction with Skin, SPA, GAIS, and PAAQ for the Safety Population.

A figure will be provided for the change from baseline of each FACE-Q™ questionnaires (Satisfaction with Facial Appearance, Aging Appraisal, Psychological Function, Social Function, and Satisfaction with Skin) in the Rasch-transformed score by treatment group and gender, for the Evaluable Population.

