8.5 Subgroup Analyses

A subgroup analysis on the primary efficacy endpoints (change from baseline in the overall Rasch-transformed score of the FACE-Q™: Satisfaction with Facial Appearance Scale to the final study visit) will be performed by gender and overall.

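### The by-gender run of the primary analysis names no male-female comparison, so it cannot answer the question that motivates it; separately, eight secondary p-values carry no multiplicity rule and should be labelled nominal

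*SAP*

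**What the plan says.** **Gender.** SAP 4.2 plans a subgroup version of the primary efficacy analysis by gender, on the ground that men and women "may have differing expectations/perceptions of aesthetic improvement; they will be examined separately". SAP 8.5 adds that this subgroup analysis "will be performed by gender and overall". SAP 8.3.3 defines the primary analysis as a one-sample t-test on change from baseline, or a Wilcoxon signed-rank test if normality fails. Neither 4.2 nor 8.5 names a between-gender contrast, an interaction term, a minimum number of men or a rule for reading the two results. SAP 8.1 makes confidence intervals one-sided 97.5% unless stated otherwise. Recruitment is to target men, but no quota or expected share is given (Protocol 4.1, SAP 2.2).

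**Secondary tests.** The general rule in SAP 8.1 is a "one-sample, one-sided t-test at 0.025 significance level", with the Wilcoxon test as fallback. In SAP 8.4.2 the change in each of four key secondary FACE-Q scores "will be analyzed using a one sample t-test (or Wilcoxon signed-rank test if normality assumptions are not met) for the Evaluable Population". The same section states: "The PAAQ will also be summarized in the transformed total score and three domains". It applies the same test to these. That makes eight secondary tests. The self-perception of age shift table is expressly untested and the aesthetic improvement scale is only described. Under "12.0 Overall Type-I Error Control" the SAP enters that the item does not apply, and the key secondary label carries no testing order.

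Protocol 11.1 says conclusions will centre on each outcome's overall results.

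**The concern.** The SAP gives a possible difference between men and women as the reason for the subgroup. Testing each gender's change against zero asks two other questions: whether women changed, and whether men changed. The p-value in the smaller group depends mainly on how small it is. If few men enrol, the likely display is a significant result in women beside a non-significant one in men, even when both respond equally. That could be read as a finding that treatment works in women but not in men. The default one-sided intervals do not help, because they bound each gender's estimate on one side only.

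The secondary tests raise a smaller issue. Protocol 3.1 states the primary objective in terms of psychological, social and emotional impact, but the scales that measure psychological and social function directly are secondary. Their p-values may well be quoted, and the plan does not say whether they are confirmatory or nominal.

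**Working it through.** **Inputs.** One-sided alpha 0.025; mean change 12.0; SD 25.0; 48 evaluable; 20% drop-out; 60 enrolled (Protocol 11.7, SAP 2.4). The standardised effect is 12/25 = 0.48. Assumptions: the number of men among the 48, shown over a range, and the same mean and SD in both genders.

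**1. The plan's own figure.** Power = P(T > t(0.975, n−1)), where T is noncentral t with n−1 degrees of freedom and noncentrality 0.48√n. This gives 90.3% at n = 48 and 89.6% at n = 47, so 48 is the minimum. Then 48/0.8 = 60. The stated sample size is reproduced.

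**2. Separate tests, identical true effect.** Apply the same formula within each gender. The genders are independent, so

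P(significant in women only) = power(women) × [1 − power(men)].

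With 6 men and 42 women: 0.859 × (1 − 0.160) = 0.72.

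**3. Width of the direct comparison.** The 95% half-width for the unadjusted difference in mean change is t(0.975, 46) × 25 × √(1/m + 1/f), where m and f are the numbers of men and women. With 6 men: 2.013 × 25 × 0.436 = 22.0 points.

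| Men / women | Power, men | Power, women | Significant in women only | Half-width of difference |
|---|---|---|---|---|
| 4 / 44 | 10% | 88% | 79% | 26 |
| 6 / 42 | 16% | 86% | 72% | 22 |
| 12 / 36 | 33% | 80% | 54% | 17 |
| 14 / 34 | 38% | 78% | 48% | 16 |
| 24 / 24 | 62% | 62% | 24% | 15 |

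Men alone would need 37 subjects for 80% power. Every half-width exceeds the assumed effect of 12 points.

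**4. Secondary tests, if no score truly changes.** For the four FACE-Q scores, independence gives 1 − 0.975⁴ = 9.6%. For eight independent scores, 1 − 0.975⁸ = 18.3%. These eight cannot be independent, because SAP 8.4.2 builds the PAAQ total from the same nine items as its domains (5, 3 and 1 items). I simulated equicorrelated normal test statistics for the four FACE-Q scores and the three domains, with the total as the 5:3:1 weighted mean of the domains (one million draws):

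| Correlation | Any of 8 | Any of the 4 FACE-Q |
|---|---|---|
| 0 | 16.9% | 9.6% |
| 0.3 | 14.0% | 8.8% |
| 0.5 | 11.6% | 7.8% |
| 0.7 | 8.9% | 6.5% |

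The correlations are assumptions; the documents give none.

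**The case against.** **On gender.** The SAP nowhere says that a p-value will be produced in each gender or that the two will be compared by significance. Protocol 11.1 points conclusions to overall results. SAP 8.1 already provides n, mean and SD by gender, and 8.4.2 plans a figure of FACE-Q change by gender, so a reader could work out the unadjusted difference. The number of men is unknown, and with equal numbers the women-only pattern falls to 24%.

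All of this stands as a limit on the point. It does not remove it. The subgroup is defined as a version of an analysis that is itself a one-sample test, so a within-gender test is the natural reading. A comparison that the SAP gives as its reason should not be left for readers to reconstruct.

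**On the secondary tests.** A reader might infer that chance secondary claims are likely, or that the missing control undermines the trial's main result. The documents support neither. There is one primary endpoint, one overall test and no interim analysis, so the primary keeps its 0.025 level. The false-positive figures hold only if every true secondary change is zero, and Protocol section 1 reports significant physical, social and psychological benefits in the earlier HARMONY study. In an open-label, single-arm Phase 4 study that promises no joint secondary claim, unadjusted secondary tests are a defensible choice.

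A reader might also blame the gender problem on the not-applicable entry in SAP 12.0. It comes from low power in men and a missing contrast, and a stricter alpha would make it worse.

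**Conclusion.** The gender point holds. The planned by-gender analysis cannot show whether men and women differ. If it is read through within-gender p-values, it would more often than not suggest a difference that does not exist when there are 12 men or fewer among 48 (54% to 79%). At 14 men the chance is about even (48%), and with equal numbers it is 24%. These figures assume a common effect of 12 with SD 25 and an assumed male count, and they treat the within-gender test as implied.

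The multiplicity point holds only in a modest form: about a 9% to 17% chance of at least one false secondary positive (correlation 0.7 down to 0), or 6.5% to 9.6% for the four FACE-Q scores alone, if nothing truly changes. It calls for a label, not for redesign.

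**What to change.** **SAP 8.5.** Report the male-female difference in mean change with a two-sided 95% confidence interval, from a linear model of change on gender and baseline score. Show each gender's mean change with a two-sided interval. State that no conclusion will be drawn from within-gender p-values. The cost is a few lines of SAP text and one model on data already collected. The drawback is an interval that will be visibly wide: about 26, 22 and 17 points either side, unadjusted, with 4, 6 and 12 men. Baseline adjustment may narrow it, but the documents give no correlation from which to say by how much. The width would show openly that the study is too small to separate the genders.

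**SAP 12.0.** Replace the not-applicable entry with a statement that the primary is the single confirmatory test and that all secondary and subgroup p-values are nominal. This costs one sentence.

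Optionally, the four key secondary FACE-Q scores could be tested in their listed order after a successful primary, each at one-sided 0.025. That leaves the primary alpha and the 48 evaluable subjects unchanged, but an early miss would block later formal claims. It is a trade-off, not a requirement. Bonferroni across all nine tests (0.025/9 = 0.0028) would cut primary power at n = 48 from 90.3% to 66.1% and is not advised.

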13.0 SAP Version History Summary

SAP Version	Date	Summary
0.1	10 May 2023	First draft
0.2	28 June 2023	Second draft
1.0	05 September 2023	Final version
1.1	28 March 2024	Revision to modify the summaries for treatment exposure and ISR based on the data collected.
2.0	03 April 2024	Revised final version
2.1	04 June 2024	Revision with modifications below: 
1. Remove Appendix D through Appendix I.2. Add Hodges Lehmann method for the confidence interval for the median of paired samples.3. Modify the missing data imputation for FACE-Q and PAAQ questionnaires.
3.0	05 June 2024	Revised final version

Appendix A. Protocol Deviations and Violations

A protocol deviation (PD) is any non-adherence to study procedures that does not result in additional risk to the subject. Protocol deviations will be reviewed and documented before database lock.

A protocol violation (PV) is any non-adherence to the protocol that may result in significant additional risk to the subject (e.g., enrollment of a subject who does not meet the study criteria). A protocol violation can also be an event of non-adherence to Good Clinical Practice (GCP) that may impact subject safety (e.g., failure to obtain proper consent before performing study procedures). Violations should be reported to the study sponsor and the Institutional Review Board (IRB) within 5 working days if they occur.

Significant PDs/PVs (equivalent to major PDs/PVs as collected in data) will be identified before database lock. Significant PDs/PVs which impact the study conduct, data validity or integrity for the study outcomes will be summarized by the following categories:

- Inclusion or exclusion criteria
- Withdrawal Criteria
- Treatment
- Concomitant Medications
- Timeframe Deviation

The number and percentage of subjects with significant PDs/PVs will be summarized for the Safety Population by gender and total, and by treatment group and overall, for the Safety Population.

All PDs/PVs will be listed for the Safety Population.

Appendix B. List of Abbreviations

Abbreviation	Definition
AE	Adverse Event
BMI	Body Mass Index
CFL	Crow's Feet Line
CI	Confidence Interval
DD	Drug Dictionary
eCRF	Electronic Case Report Form
FHL	Forehead Line
FWS	Facial Wrinkle Scale
GAIS	Global Aesthetic Improvement Scale
GCP	Good Clinical Practice
GL	Glabellar Line
ICF	Informed Consent Form
IRB	Institutional Review Board
ISR	Injection Site Response
max	Maximum
min	Minimum
mITT	Modified Intent-to-treat
mL	Milliliter
MedDRA	Medical Dictionary for Regulatory Activities
PAAQ	Periorbital Aesthetic Appearance Questionnaire
PD	Protocol Deviation
PT	Preferred Term
PV	Protocol Violation
SAE	Serious Adverse Event
SAP	Statistical Analysis Plan
SD	Standard Deviation
SEM	Standard Error of Mean
SOA	Schedule of Activities
SOC	System Organ Class
SPA	Self-Perception of Age
SPP	Statistical Programming Plan

Abbreviation	Definition
TEAE	Treatment-emergent Adverse Event
TESAE	Treatment-emergent Serious Adverse Event
WHO	World Health Organization

Appendix C. Changes to Protocol-planned Analyses

Protocol Planned Analysis	Modified Analysis
All efficacy analyses will be based on the mITT and Evaluable Populations.	All efficacy analyses will be based on the Evaluable Populations.
Subgroup analysis by gender and treatment touch-ups.	Subgroup analysis by gender only.
mITT (modified Intent-to-Treat) Population - all subjects who enrolled and had at least one post-baseline efficacy assessment.	mITT (modified Intent-to-Treat) Population - all subjects who enrolled and had at least one post-baseline efficacy assessment at V7.
Evaluable Population– all subjects as defined in the mITT Population who have received both study products as treatments in this study, had at efficacy assessment at the final visit (V7) and no major protocol violations or deviations.	Evaluable Population– all subjects as defined in the mITT Population who have received both study products as treatments in this study, had at efficacy assessment at the final visit (V7) and no major protocol violations or deviations that will affect any efficacy endpoint.
Exploratory efficacy analysis may be performed on the collected video and photographs.	Removed.
